3. STUDY DESIGN

3.1 DESCRIPTION OF STUDY

This is a multicenter, international, randomized, open-label, Phase II trial with two study arms. A total of approximately 152 patients with advanced or metastatic ER+/HER2– breast cancer who have experienced recurrence or progression of their disease while receiving AI therapy for advanced or metastatic disease or who have relapsed within 6 months after completing adjuvant AI therapy will be enrolled in this study. Patients who are enrolled in Arm A will receive GDC-0810, administered at 600 mg PO daily. Patients who are enrolled in Arm B will receive fulvestrant, administered at 500 mg intramuscularly on Days 1 and 15 of Cycle 1, and Day 1 of each subsequent 28-day cycle thereafter.

A permuted block randomization scheme will be used to ensure an approximate 1:1 allocation of patients who receive GDC-0810 (Arm A) versus patients who receive fulvestrant (Arm B) with respect to two stratification factors per local assessment: geographic region (United States, European Union, and Rest of World) and presence or absence of visceral disease.

Patients may have either measurable disease (per RECIST v1.1) and/or non-measurable, but evaluable, locally advanced or metastatic disease with at least one evaluable bone lesion. Locally advanced disease must not be amenable to resection or

other local therapy with curative intent (see Section 4.1.1 and Section 4.1.2 for detailed inclusion and exclusion criteria).

Patients will receive study treatment in 28-day cycles until documented radiographic disease progression, intolerable toxicity, elective withdrawal from the study, study completion, or study termination. Tumor assessments will be conducted for all patients at screening, *per institutional guidelines, and as clinically indicated*. A schedule of study assessments is provided in [Appendix 1](#) and [Appendix 2](#).

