4.2 METHOD OF TREATMENT ASSIGNMENT

After written informed consent has been obtained and eligibility has been established and approved, the study site will obtain the patient's identification number and treatment assignment from the Interactive Web Response System (IWRS). Patients will be randomized to receive either GDC-0810 or fulvestrant in an approximate 1:1 ratio through the use of a permuted block randomization method.

Randomization will be stratified by the following criteria:

- Visceral versus non-visceral disease:
 - Visceral disease: metastatic disease in the lung, liver, adrenal glands, brain, heart, pericardium, pleura, peritoneum, or other organs of the chest, abdomen and pelvis
 - Non-visceral disease: absence of metastatic disease in visceral organs. Pleural effusions and/or ascites. Disease involving lymph nodes and disease involving bone are not considered to be visceral disease.

- Geographical region:
 - United States
 - European Union
 - Rest of World (remaining countries)

The Sponsor, the investigators, and the patients will be unblinded to treatment assignment.

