6.1 DETERMINATION OF SAMPLE SIZE

The trial is designed to evaluate the clinical activity and safety of GDC-0810 compared with fulvestrant in patients with ER-positive locally advanced or MBC. It is for hypothesis generation, and is not powered to detect minimum clinically meaningful difference between treatment arms.

A total of approximately 152 patients will be enrolled in this study. It is assumed that the median duration of PFS in the fulvestrant control arm is 5.5 months and 8.5 months in the GDC-0810 arm. The final analysis of all randomized patients will be triggered by the occurrence of approximately 95 PFS events, which is expected to occur 26 months after the first patient is randomized. [Table 4](#) shows expected probabilities of observing a hazard ratio of less than 0.5, 0.6 and 0.7 in the final analysis in all randomized patients under varying assumptions for the true underlying hazard ratio. Note that formal hypothesis testing is limited. Rather than testing treatment differences at a statistically significant type I error level of 5%, 90% confidence intervals (CI) for the hazard ratio will be calculated.

At a target hazard ratio of 0.6, the corresponding 90% CI based on 95 PFS events is (0.43, 0.84) which is considered to provide meaningful precision.

Table 4 Expected Probability of Observing a Hazard Ratio of <0.5, <0.6, or <0.7 in the Final Analysis (All Patients)

True HR	95 PFS Events in ITT Population		
	Observed HR < 0.50	Observed HR < 0.60	Observed HR < 0.70
0.4	0.86	0.98	0.99
0.5	0.50	0.81	0.95
0.6	0.19	0.50	0.77
0.7	0.05	0.23	0.50
0.8	0.01	0.08	0.26

HR=hazard ratio; ITT=intent to treat; PFS=progression-free survival.

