6.4.2 Secondary Efficacy Endpoints

6.4.2.1 Objective Response Rate

The analysis of ORR will only include patients who have measurable disease at baseline (and will thus exclude patients with bone-only disease). An estimate of the response rate and its 90% CI will be calculated using the Blyth-Still-Casella method for each treatment arm. Response rate in the treatment arms will be compared using the stratified Mantel-Haenszel test. CIs for the difference in ORRs between the two arms will be determined using the normal approximation to the binomial distribution.

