6.4.2.3 Clinical Benefit Rate

CBR is defined as the percentage of patients who experience a CR, PR, or SD lasting for at least 24 weeks since randomization. An estimate of CBR and its 90% CI will be calculated using the Blyth-Still-Casella method for each treatment arm. The CBRs in the treatment groups will be compared using the stratified Mantel-Haenszel test. CIs for the difference in CBR between the two arms will be determined using the normal approximation to the binomial distribution.

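### ORR and CBR have a stratified test but no matching stratified interval for the difference; the interval can be slightly wider than needed and can disagree with the test

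*Combined protocol and SAP*

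**What the plan says.** Randomization uses "two stratification factors per local assessment: geographic region (United States, European Union, and Rest of World) and presence or absence of visceral disease" (section 3.1), which makes six cells.

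On CBR, section 6.4.2.3 states that "The CBRs in the treatment groups will be compared using the stratified Mantel-Haenszel test" and then that "CIs for the difference in CBR between the two arms will be determined using the normal approximation to the binomial distribution". On ORR, section 6.4.2.1 states that "Response rate in the treatment arms will be compared using the stratified Mantel-Haenszel test" and then that "CIs for the difference in ORRs between the two arms will be determined using the normal approximation to the binomial distribution". The per-arm rates get a 90% interval in both sections. The intervals for the differences have no stated level, and neither test has a stated significance level.

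For PFS (section 6.4.1) the log-rank test and the Cox model that gives the hazard ratio and its 90% CI use the same stratification factors, and unstratified results are promised in addition. Sections 6.4.2.1 and 6.4.2.3 have no such pairing and no supportive analysis.

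**The concern.** The test conditions on the randomization strata, while the interval beside it apparently does not. If response differs between strata, a simple two-sample variance still contains between-stratum variation that the stratified design and test have removed. Section 3.3.1 stratifies by visceral disease because it is an unfavorable prognostic factor, so some gap in response is plausible.

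Two things are at stake. Some precision may be given away in the reported difference. And one table row could carry a p-value and an interval that point in different directions, with no stated rule on which one governs.

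**Working it through.** **Inputs from the documents.** "A total of approximately 152 patients will be enrolled in this study" (section 6.1) and "Patients will be randomized to receive either GDC-0810 or fulvestrant in an approximate 1:1 ratio" (section 4.2), so about 76 per arm. Fulvestrant CBR 32%-42% (section 1.4). Six strata (section 3.1).

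**Assumptions not in the documents.** Half the patients have visceral disease and regions are equal in size; the response gap between visceral strata is 0 to 30 points, plus one extreme case; the interval for the difference is 90%; the test is two-sided 10%; ORR is 5%-20% in 90-120 patients with measurable disease, with an 8-point gap.

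**The plan's own precision figure.** None is given for ORR or CBR. The nearest is the 90% CI for a PFS hazard ratio of 0.6 with 95 events: exp(ln 0.6 ± 1.645 × 2/√95) = (0.428, 0.841), which reproduces the stated (0.43, 0.84).

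**Width.** With two equal strata a gap g apart and no treatment effect, the pooled variance p(1−p) equals the mean within-stratum variance plus g²/4. The ratio of unstratified to stratified width is therefore √[p(1−p) / (p(1−p) − g²/4)].

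| CBR | Gap | Calculation | Excess width |
|---|---|---|---|
| 32% | 0 | ratio 1 | 0% |
| 32% | 20 points | √(0.2176/0.2076) | 2.4% |
| 32% | 30 points | √(0.2176/0.1951) | 5.6% |
| 42% | 20 points | √(0.2436/0.2336) | 2.1% |
| 42% | 30 points | √(0.2436/0.2211) | 5.0% |

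Simulation (20,000 trials per scenario, six strata, Mantel-Haenszel difference with Sato variance) agrees. At a CBR of 32% the mean full widths are 0.247 against 0.242 at a 20-point gap, and 0.247 against 0.234 at 30 points (5.7%). Only a 40-point visceral gap combined with a 20-point region gap reaches 11%-13%.

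For ORR the simulated excess was 0.4%-0.8%; the runs available assumed a 10-point effect. The formula with no effect gives 0.5% at an ORR of 20% (√(0.16/0.1584)) and 0.9% at 10% (√(0.09/0.0884)). At 5%, where an 8-point gap means 9% against 1%, it gives 1.7% (√(0.0475/0.0459)).

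**Coverage of the unstratified 90% interval for CBR.** It is 89%-90% at gaps of 0-20 points, about 91% at 30 points and 93% in the extreme case.

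**A contradictory row.** Take two strata of 38 per arm: GDC-0810 26 and 14 responders, fulvestrant 21 and 9.

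- Difference: 40/76 − 30/76 = 0.1316.
- Stratified test: observed minus expected = 40 − 35 = 5; variance = 4.543 + 4.063 = 8.607; z = 5/√8.607 = 1.70; p = 0.088.
- Unstratified 90% CI: SE = √(0.5263 × 0.4737/76 + 0.3947 × 0.6053/76) = 0.0802, giving (−0.0003, 0.263), which includes 0.
- Stratified 90% CI: SE = √[(0.01219 + 0.01088)/4] = 0.0759, giving (0.007, 0.257), which excludes 0.

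**How often, for CBR at the assumed 10% test level.** With a 15-point effect, test and unstratified interval disagree in 1.8%-3.1% of trials at gaps of 0-20 points and 2.6%-4.6% at 30 points. Separate simulations with 55% visceral, CBR 25-30% against 55-60% and a 12-point effect gave 4%-6%. With no effect the figures are 0.7%-1.2% and 1.4%-1.6%. A stratified interval lowers disagreement to 0.4%-1.4%. In the ORR runs available it is about 1%-2% with either interval.

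**Unstated level.** In the scenario run, a 5% test beside a 90% unstratified interval disagrees in 5.3% of trials with no effect and 11.4% with a 15-point effect. Stratifying the interval does not cure this (5.8% and 13.2%).

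**The case against.** The strongest reply is that the plan never calls the interval unstratified. A Mantel-Haenszel-weighted difference with a Wald interval also rests on a normal approximation to binomials. This stands: what can be shown is an interval not tied to the strata, most naturally read as the simple one.

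A reader might infer that the planned interval is simply too wide. The documents do not support that. They give no CBR or ORR by visceral status; section 3.3.1 speaks of survival, not response, and the 30-point gap is an assumption. With no gap the two widths are equal and coverage is at or slightly below 90%.

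A reader might also take section 6.1 to mean that this trial reports intervals instead of tests throughout. That sentence concerns the PFS hazard ratio only, and section 6.4.1 names the log-rank test as the primary analysis.

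Nor is every disagreement due to the strata. With small gaps most run the other way, because the Wald interval uses an unpooled variance. For 36/76 against 26/76 with equal strata, the interval is (0.002, 0.262) and p = 0.101. A stratified interval leaves a remainder.

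Finally, the simple difference equals the difference of the two per-arm rates printed beside it, and a weighted one need not. That is a real but small cost. It does not outweigh a matching test and estimate, which the plan already has for PFS.

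**Conclusion.** The concern holds as a mismatch and under-specification with a small effect. The tests for ORR and CBR are stratified; the intervals for the difference, as naturally read, are not, and have no stated level. The unstratified interval is valid. For CBR it is about 0-2.4% wider than a stratified one at assumed visceral gaps up to 20 points and about 5-6% wider at 30 points. For ORR the excess is under 1% in the simulated scenarios, and slightly above only when ORR is near 5% with no effect.

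With a 12-15-point CBR effect and a 10% test, disagreement within a row is roughly 2-5% of trials, against about 0.5-2% with a stratified interval. These rates depend on the assumed gaps, stratum shares and test level, so they show order of magnitude only.

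Severity is minor. Both endpoints are secondary; the trial is described as hypothesis generating and unpowered (section 6.1) and makes no multiplicity adjustment (section 6). Development is halted and enrollment discontinued (sections 2 and 3.1), so the analysed number may be well below 152. The width ratio in the formula does not depend on sample size, but sparse cells become more likely.

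**What to change.** In sections 6.4.2.1 and 6.4.2.3:

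- Report the Mantel-Haenszel-weighted risk difference with a stratified 90% CI, using the same strata as the test. Name the variance formula; the calculations here used the Sato variance, and other stratified intervals were not checked.
- State the corresponding test level, two-sided 10%.
- Keep the unstratified interval as supportive, as section 6.4.1 does for PFS.
- Pre-specify when region cells count as too sparse. In that case, collapse to visceral disease alone for both the test and the interval; collapsing only one would recreate the mismatch.
- Note under the table that the weighted difference may not exactly equal the difference of the per-arm rates.

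The cost is a few sentences per section and standard software, with no additional data.

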6.5 SAFETY ANALYSES

The safety analyses will include all randomized patients who received at least one dose of study drug, with patients grouped according to the treatment actually received. Safety will be assessed through summaries of adverse events, changes in laboratory test results, changes in vital signs, and GDC-0810 exposure.

Drug exposure will be summarized, which includes duration of treatment, number and intensity of dose.

Verbatim descriptions of adverse events will be mapped to thesaurus terms. Adverse-event data will be listed by study site, treatment arm, patient number, and study day. All adverse events occurring during or after the first dose of study treatment will be summarized by thesaurus term, appropriate thesaurus levels, treatment arm, and NCI CTCAE v4.0 grade. In addition, serious adverse events, severe adverse events (Grade ≥ 3), adverse events of special interest, and adverse events leading to study drug discontinuation or interruption will be listed separately and summarized accordingly. Multiple occurrences of the same event will be counted once at the maximum severity.

Deaths reported during the study will be summarized by treatment arm, including reasons leading to death.

Relevant laboratory and vital sign (heart rate, blood pressure, and temperature) data will be displayed by time, with NCI CTCAE Grades 3 and 4 values identified, where appropriate. Additionally, all laboratory data will be summarized by NCI CTCAE v4.0 grade.

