2.2 SAFETY OBJECTIVES

The safety objective for this study is as follows:

- To evaluate the safety and tolerability of GDC-0810 compared with fulvestrant, focusing on the nature, frequency, and severity of serious and non-serious adverse events

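### Section 6.5 offers only crude once-per-patient adverse event summaries for a between-arm comparison of frequency, with no allowance for time at risk that can differ by arm

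*Combined protocol and SAP*

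**What the plan says.** Section 2.2 sets a comparative objective that names frequency: "To evaluate the safety and tolerability of GDC-0810 compared with fulvestrant, focusing on the nature, frequency, and severity". Section 6.5 gives the method: "All adverse events occurring during or after the first dose of study treatment will be summarized by thesaurus term, appropriate thesaurus levels, treatment arm", and also by grade. The counting rule is "Multiple occurrences of the same event will be counted once at the maximum severity". No exposure-adjusted rate, time-to-first-event analysis or fixed-window incidence is named, and no between-arm test or interval for adverse events is planned. Exposure appears as a separate summary: "Drug exposure will be summarized, which includes duration of treatment, number and intensity of dose".

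The length of observation is set elsewhere. Section 3.1 says "Patients will receive study treatment in 28-day cycles until documented radiographic disease progression, intolerable toxicity", and adds withdrawal and study end as further reasons to stop. Section 5.3.1 collects adverse events up to 28 days after the last dose. Section 6.1 states "It is assumed that the median duration of PFS in the fulvestrant control arm is 5.5 months and 8.5 months in the GDC-0810 arm". The documents give no expected treatment duration.

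**The concern.** The proportion of patients who ever have an event depends on the risk per unit time and on how long they are watched. Here the watching stops 28 days after treatment does, and treatment mostly stops at progression. If one arm progresses later, its patients have longer to record a first event, and a crude proportion credits that extra time to the drug. The separate duration summary alerts a reader to the difference but does not allow a fair comparison for any particular event.

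What is at stake is misreading, not a false rejection, since no test is planned. If GDC-0810 delayed progression as assumed, it could look more toxic at equal risk; if its patients stopped earlier, its toxicity could be understated. The events most exposed to this are those that may arise at any time on treatment. The special-interest list in Section 5.2.3 includes thromboembolism, transaminase elevation and vaginal or uterine hemorrhage, and the protocol does not describe these as confined to early cycles.

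**Working it through.** **The plan's own figure.** The plan gives no figure for adverse event incidence. Its stated precision for PFS does reproduce: exp(ln 0.6 ± 1.645 × 2/√95) = (0.428, 0.841), against the stated (0.43, 0.84).

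**Inputs from the documents.** Median PFS 5.5 and 8.5 months, and final analysis 26 months after the first randomization (Section 6.1); enrollment over about 22 months (synopsis, Length of Study); reporting to 28 days after the last dose (Section 5.3.1).

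**Assumptions.** Exponential PFS, time on treatment equal to PFS, uniform accrual, no dropout, and an adverse event hazard μ that is constant and equal in the two arms. The documents give no adverse event hazard, so μ is varied from 2% to 10% per month.

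**Step 1, time at risk.** λ = ln 2/median, which is 0.1260 per month for fulvestrant and 0.0815 for GDC-0810. The window is w = 28/30.4375 = 0.92 months. Potential follow-up u is uniform from 26 − 22 = 4 to 26 months. Mean time at risk is w plus the average over u of [1 − exp(−λ(u − w))]/λ.
- Fulvestrant: 7.03 months
- GDC-0810: 8.75 months
- Ratio: 1.24

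**Step 2, crude incidence at equal hazard.** This is the average over u of 1 − e^(−μw) + e^(−μw) × μ/(μ + λ) × [1 − e^(−(μ+λ)(u−w))].

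| μ per month | Fulvestrant | GDC-0810 | Excess (unrounded inputs) | Ratio |
|---|---|---|---|---|
| 2% | 12.7% | 15.5% | 2.8 points | 1.22 |
| 5% | 27.6% | 32.9% | 5.3 points | 1.19 |
| 10% | 45.1% | 52.0% | 6.8 points | 1.15 |

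**Step 3, early events.** If the hazard exists only in cycle 1, the 28-day window keeps every patient at risk throughout that cycle and the crude ratio is 1.00. Ignoring the window, it is about 1.02. For a hazard limited to the first three cycles, again ignoring the window, it is about 1.05 to 1.06.

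**Step 4, patient-year rates.** For a low-incidence event confined to cycle 1, with equal toxicity, the rate ratio is about 1.00/1.24 = 0.80. The longer-exposed arm would look safer than it is.

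**Step 5, a fixed time of 24 weeks.** 168/30.4375 = 5.52 months. With the end of the reporting period as a competing event, put u = 5.52 in the step 2 formula without averaging. This gives 8.4% vs 9.0%, 19.6% vs 21.0% and 34.9% vs 37.2%, an excess of 0.6 to 2.4 points. If patients are instead censored at that point, and censoring is independent of the event, both arms give 1 − exp(−5.52μ): 10.5%, 24.1% and 42.4%.

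**Limit of the model.** Under these assumptions about 111 PFS events would be expected by 26 months, against the 95 stated. Dropout of about 30% a year would give 94.6, and slower accrual could also explain the gap. Either would change the exposure figures.

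**The case against.** The strongest reply has four parts.

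- **The tables are descriptive.** Section 6.1 describes a hypothesis-generating trial, and Section 6.5 plans no adverse event test. With 76 patients per arm, a two-sided 5% test would flag gaps of this kind only about 5% to 15% of the time. Readers also get treatment duration, listings by study day, and laboratory and vital-sign data over time, and Section 6.6 allows population PK/PD work on safety. This stands as a limit on consequence. It does not supply a frequency comparison that allows for time at risk.
- **The identified risks are early.** Section 5.1.3.1 says most gastrointestinal events were seen as early as the first cycle. Step 3 shows almost no distortion if risk is confined there. This stands, so the point concerns events with a continuing hazard.
- **Patient-year rates can mislead in the opposite direction.** Step 4 confirms it, so they are unsuitable as the main measure.
- **The planned trial will not be completed.** Section 2 says development and enrollment have stopped and the primary objectives will not be met. This stands: the figures describe the design as planned.

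A reader might also infer from 8.5/5.5 = 1.545 that treatment is expected to last 55% longer on GDC-0810. With every patient followed to progression and no window, μ/(μ + λ) gives 13.7% vs 19.7%, 28.4% vs 38.0% and 44.2% vs 55.1%, an excess of 6 to 11 points. The documents do not support that reading. The 55% is a ratio of assumed PFS medians; treatment also stops for toxicity, withdrawal or patient or investigator decision (Sections 3.1 and 4.6.2); and the 26-month cutoff cuts exposure short.

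**Conclusion.** The point holds at a modest size. Section 6.5 answers a comparative question about frequency with a measure that ignores time at risk, and the plan's own PFS assumption implies that this time differs by arm. Under the planned design and the stated assumptions, time at risk is about 24% longer on GDC-0810, and events with an equal continuing hazard of 2% to 10% per month gain about 3 to 7 points. Events confined to the first cycle gain almost nothing.

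It would be wrong to conclude that GDC-0810 will in fact look more toxic than it is. Under Section 3.1 the remaining patients may also stop when GDC-0810 supply runs out or the sponsor ends the study, so the actual imbalance could run either way. That uncertainty is itself a reason not to rest frequency comparisons on crude proportions alone.

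**What to change.** Keep the crude tables. Add to Section 6.5, for adverse events of special interest, serious events and Grade 3 or higher events, the cumulative incidence of first event by arm at a fixed time such as 24 weeks, the horizon already used for clinical benefit. Censor at data cutoff. Handle death and the end of the adverse event reporting period as competing events or by another stated rule. Step 5 shows why the rule must be written down: treating the end of reporting as a competing event reduces the distortion but leaves some of it, while censoring there removes it only if censoring is independent of the event. Report the between-arm difference with a 90% CI, and base between-arm frequency statements for these events on that table.

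Patient-year rates may be shown as supplementary, with a note that they assume a roughly constant hazard and favour the longer-exposed arm for early-onset events.

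The cost is one extra descriptive table from data already collected. Its intervals will be wide after the early halt.
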